7.2.1.2. Summary Measure

Overall response rate (ORR) and the associated 2-sided 95% exact confidence intervals will be provided by dose level and study part. In addition, Clinical Benefit Rate (CBR), defined as the percentage of subjects with minimal response (\geq MR) will be summarized in the same way as ORR by dose level and study part. Unconfirmed response summaries may be provided for interim analyses. A list of investigator-assessed response at each visit will be listed.

7.2.1.3. Population of Interest

The secondary efficacy analyses will be based on the “All Treated” population, unless otherwise specified. Response data for multiple myeloma will be summarized by Study Part using the All Treated MM population and in subgroup: Prior anti-cancer therapy of interest as defined in Section 5.2.1.

7.2.2. Lymphoma

7.2.2.1. Endpoint / Variables

7.2.2.1.1. Overall Response Rate

For lymphoma patients, clinical activity for lymphomas will be calculated based on ORR defined as the percentage of subjects with confirmed CR or PR, as described in the Revised Response Criteria for Malignant Lymphoma (RRCML, Appendix 2 in the protocol) from the start of treatment until disease progression or the start of new anti-cancer therapy.

A summary of investigator-assessed best response with confirmation will be presented. Subjects with Not Evaluable or missing response will be treated as non-responders; and they will be included in the denominator when calculating the percentage. To be assigned a status of complete response or partial response, all responses must be confirmed by repeat assessments performed no less than four weeks after the criteria for CR or PR were met (RRCML, Appendix 2 in the protocol).

7.2.2.2. Summary Measure

Overall response rate and the associated 2-sided 95% exact confidence intervals will be provided. A list of investigator-assessed response at each visit will be listed.

7.2.2.3. Population of Interest

The secondary efficacy analyses will be based on the “All Treated” population, unless otherwise specified. Response data for lymphoma will be summarized using the Part 2 NHL population.

7.2.3. Strategy for Intercurrent (Post-Randomization) Events

Not applicable to this study.

7.2.4. Statistical Analyses / Methods

Details of the planned displays are provided in [Appendix 12](#): List of Data Displays and will be based on GSK data standards and statistical principles.

Unless otherwise specified, endpoints / variables defined in Section 7.2.1 will be summarised using descriptive statistics, graphically presented (where appropriate) and listed.

7.3. Exploratory Efficacy Analyses

7.3.1. Multiple Myeloma

7.3.1.1. Endpoint / Variables

Time-to-event endpoint - Multiple Myeloma	
Progression-Free Survival (PFS)	defined as the time from first dose until the earliest date of confirmed disease progression (PD) per IMWG (2011), or death due to any cause.
Time to Progression (TTP)	defined as the time from first dose until the earliest date of PD per IMWG (2011), or death due to PD.
Duration of Response (DOR)	defined as the time from first documented evidence of confirmed PR or better until the time when disease progression (PD) is documented per IMWG (2011), or death due to PD among subjects who achieve a response (i.e. confirmed PR or better).
Time to Response (TTR)	defined as the time between the date of first dose and the first documented evidence of confirmed response (PR or better), among subjects who achieve a response (i.e., confirmed PR or better).
Time to Best Response (TTBR)	defined as the time between the date of first dose and the best confirmed response (PR or better), among subjects who achieve a response (i.e., confirmed PR or better).
Overall survival (OS)	defined as the time from the date of first dose until death from any cause.

In addition, monoclonal protein and serum free light chain lab test values will be plotted. Subgroup analysis for ORR will be performed

7.3.1.2. Summary Measure

7.3.1.2.1. Progression-Free Survival

PFS is defined as the interval of time between the date of first dose and the earlier of the date of first disease progression and the date of death due to any cause. Disease progression will be based on the assessments by the Investigator.

If there is no adequate baseline assessment, the subjects will be censored at their date of first dose. Subjects without any adequate post-baseline tumor assessments will be censored at the date of first dose.

Subjects who progressed or died after an extended period without adequate assessment will be censored at their date of last adequate assessment prior to progression or death even if subsequent information is available regarding progression or death. An adequate assessment is defined as an assessment where the Investigator determined response is sCR, CR, VGPR, PR, MR or SD. The date of response at that assessment will be used for censoring. As the assessment schedule may change through the course of the protocol, specific rules for identifying extended loss to follow-up or extended time without an adequate assessment are provided in Section 16.5.4.

For subjects who receive subsequent anti-cancer therapy the following rules will apply:

- If the start date of the anti-cancer therapy is partial (i.e. either missing the day but has the month and year available or missing both day and month), the imputation rules described in Section 16.7.2.1 will be applied. No imputation will be made for completely missing dates.
- If anti-cancer therapy is started without documented disease progression or death OR is started prior to documented disease progression or death, then PFS will be censored at the date of the last adequate assessment that is no later than the date of initiation of anti-cancer therapy (i.e. if an assessment occurs on the same day as the start of new anti-cancer therapy the assessment will be used - as it will be assumed the assessment occurred prior to the administration of new anti-cancer therapy). The date of response at the last adequate assessment will be used as the censoring value.
- If a subject has only a baseline visit or does not have an adequate assessment that is no later than the date of initiation of anti-cancer therapy, PFS will be censored at the date of first dose.
- If a subject has neither progressed nor died nor started new anti-cancer therapy, then PFS will be censored at the date of the last adequate assessment defined as an assessment where the Investigator determined response is sCR, CR, VGPR, PR, MR or SD. The date of response will be used as the censoring date.

A summary of the assignments for progression and censoring dates for PFS are specified in Table 5.

Table 5 Assignments for Progression and Censoring Dates for PFS Analysis

Situation	Date of Event (Progression/Death) or Censoring	Outcome Event (Progression/Death) Or Censored
No (or inadequate) baseline tumor assessments ^[1] and the subject has not died (if the subject has died follow the rules for death indicted at the bottom of the table)	First dose date	Censored
No post-baseline assessments and the subject has not died (if the subject has died follow the rules for death indicted at the bottom of the table)	First dose date	Censored
Progression documented between scheduled visits	Date of assessment of progression ^[1]	Event
No progression (or death)	Date of last 'adequate' assessment of response ^[2]	Censored
New anticancer treatment started (prior to documented disease progression or death) ^[3] .	Date of last 'adequate' assessment of response ^[2] (on or prior to starting anti-cancer therapy)	Censored
Death before first PD assessment (or Death at baseline or prior to any adequate assessments)	Date of death	Event
Death between adequate assessment visits	Date of death	Event
Death or progression after an extended loss-to-follow-up time (two or more missed cycles + 7 day window) ^[4]	Date of last 'adequate' assessment of response ^[2] (prior to missed assessments)	Censored

[1] **In part 1**, adequate baseline assessment is defined as at baseline, a patient has at least one of the following measurements: a. Serum M-protein or b. Urine M-protein or c. Serum FLC assay or d. Biopsy proven plasmacytoma (should be measured within 28 days of Screening Visit).

In part 2, adequate baseline assessment is defined as at baseline, a patient has at least one of the following measurements: a. Serum M-protein ≥ 0.5 g/dL (≥ 5 g/L) or b. Urine M-protein ≥ 200 mg/24h or c. Serum FLC assay: Involved FLC level ≥ 5 mg/dL (≥ 50 mg/L) and an abnormal serum free light chain ratio (<0.26 or >1.65) or d. Biopsy proven plasmacytoma (should be measured within 28 days of Screening Visit and no later than the first dose date).

[2] An adequate assessment is defined as an assessment where the Investigator determined response is sCR, CR, VGPR, PR, MR, or SD.

[3] If PD or death and New anti-cancer therapy occur on the same day assume the progression or death was documented first (e.g., outcome is progression or death and the date is the date of the assessment of progression or death). If anti-cancer therapy is started prior to any adequate assessments, censoring date should be the date of first dose.

[4] Refer to section 16.5.4 "Extended Loss to Follow-up or Extended Time without an Adequate Assessment".

PFS will be summarized using Kaplan-Meier curves. If there are a sufficient number of progressions or deaths, median PFS, first and third quartiles and 95% CI, will be estimated using the Brookmeyer-Crowley method [Brookmeyer, 1982]. A figure and listing of PFS time will also be provided. Summary and figure of PFS will be based on

Part 2 MM sub-population and subgroup prior anti-cancer therapy of interest; listing of PFS will be based on All Treated MM population.

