6.5. Extent of Exposure

Extent of exposure to GSK2857916 will be summarized.

The number of cycles administered to study treatment will be summarised with mean, median, standard deviation, minimum, and maximum. The number and percentage of subjects who received a given number of cycles (<4, 4, and >4 cycles) will be reported.

Dose intensity (dose delivered per cycle) will be summarized using mean, median, standard deviation, minimum, and maximum by cycle and overall. Dose intensity is the cumulative actual dose divided by the total number of cycles across the entire treatment period. A by subject summary listing of data on exposure to all study treatments will be produced.

Dose reductions will be summarised by number of reductions and reasons for reductions. Dose delays will be summarised by number of delays, reasons for the delays, and delay duration (days). The number and percentage of the delays 1-21, 22-42 and >42 days will be computed. Primary reasons for dose reductions and dose delays will also be summarized by cycle.

Duration of delays is defined as period from the expected start date of dose to actual start date of current dose. Calculation: (actual start date of current dose - expected start date of dose). Expected start date of dose = actual start date of previous dose + 21.

The summaries of dose modifications will be provided only if the data warrant.

All the dose reductions, dose escalations, infusion interruptions, incomplete infusions and dose delays will be listed separately.

A plot showing the number and percentage of subjects treated at different dose levels over time will be provided.

The duration of exposure to study treatment in days (from first day to last day of treatment) will be calculated. A horizontal bar graph of duration of treatment will be produced that displays duration of treatment in days for each subject.

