16.5.4. Extended Loss to Follow-up or Extended Time without an Adequate Assessment

For subjects, if two or more scheduled disease assessments are missed and are then followed by an assessment of PD or death, PFS will be censored at the last adequate assessment prior to PD or death. When the scheduled disease assessment is every 3 weeks, a window of 49 days (6 weeks + 7 day window) will be used to determine whether there was an extended time without adequate assessment. That is, if the time difference between PD/death and last adequate assessment is more than 49 days, then PFS will be censored at the last adequate assessment prior to PD/death.

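### The PFS censoring text contradicts Table 5 on early progression and death, and the 49-day rule can censor a progression after a dose delay with no assessment missed

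*SAP*

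**What the plan says.** **First-dose censoring.** SAP Section 7.3.1.2.1 defines PFS as ending at "the earlier of the date of first disease progression and the date of death due to any cause". It then states: "Subjects without any adequate post-baseline tumor assessments will be censored at the date of first dose". The meaning of adequate follows: "An adequate assessment is defined as an assessment where the Investigator determined response is sCR, CR, VGPR, PR, MR or SD". PD is not on that list.

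Table 5, in the same section, differs. Apart from inadequate baseline, its day-0 row covers "No post-baseline assessments and the subject has not died". A separate row, "Death before first PD assessment (or Death at baseline or prior to any adequate assessments"), is an event at the date of death. The progression row reads "Progression documented between scheduled visits" and is an event at the assessment date. Its counterpart for TTP (Table 6) also covers progression at a scheduled visit.

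**Extended gap.** Section 16.5.4 introduces this censoring for two or more missed scheduled disease assessments and sets a window of 6 weeks plus 7 days. It then applies the window to elapsed time: "if the time difference between PD/death and last adequate assessment is more than 49 days, then PFS will be censored" at the last adequate assessment. Table 6 carries the same extended-loss row, and Section 7.3.1.2.3 makes DOR follow the TTP censoring rules.

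**Calendar.** Section 16.2.3.1 places the myeloma disease laboratory tests at the start of each 21-day cycle. Section 6.5 dates the expected next dose 21 days after the actual previous one and provides categories for long delays: "The number and percentage of the delays 1-21, 22-42 and >42 days will be computed".

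**The concern.** The two statements of the PFS rule give different answers for the same subject. Two programmers could follow the text and the table respectively, and both could claim compliance. The subjects affected are those with the worst course: disease that progresses at the first assessment, or death before any adequate assessment. Censoring them at time zero removes them from the risk set before they contribute an event, so the Kaplan-Meier curve moves up.

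The 49-day rule raises a different problem. It is meant for lost follow-up, but elapsed time also grows when a dose is held. If disease assessments move with the dose, a subject seen at every cycle start can still have a progression censored. Subjects held off drug are unlikely to be a random sample, so that censoring may be informative. It also carries into TTP and DOR.

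**Working it through.** **Day-0 rule, passages side by side**

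| Situation | Text sentence | PFS definition | Table 5 |
|---|---|---|---|
| First post-baseline assessment is PD | Censored, day 0 | Event | Outside the day-0 row, since an assessment exists; the PD row names only PD between scheduled visits |
| Death before any adequate assessment | Censored, day 0 | Event | Event at death |
| Alive, no post-baseline assessment | Censored, day 0 | No event | Censored, day 0 |

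The text agrees with Table 5 only in the last line. PD at the first scheduled visit has no explicit row in Table 5.

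**Size if the text is programmed.** The SAP gives no early-PD rate, so the rate is assumed. Let k of n subjects be early events moved to censoring at day 0, with f = k/n and no other early censoring. After the first assessment the reported curve is S(t)/(1 − f). Take n = 40, the maximum in Section 3.1.2.1.1. A true PFS of 50% is then reported as:

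- k = 2 (5%): 0.5/0.95 = 52.6%
- k = 4 (10%): 0.5/0.90 = 55.6%
- k = 8 (20%): 0.5/0.80 = 62.5%

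For an exponential curve, setting S(t)/(1 − f) = 0.5 multiplies the median by 1 + log2(1/(1 − f)), which is 1.07, 1.15 and 1.32.

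A simulation with exponential PFS, visits every 21 days and no delays moved the median from 3.45 to 4.14, 6.21 to 6.90 and 12.42 to 13.11 months (true medians 3, 6 and 12). Each shift is 0.69 months = 21/30.4375, one visit interval. In 2000 simulated trials of 40 (true median 6 months) the rule raised the median in 69%, left it unchanged in 31% and never lowered it.

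A cluster of early progressors gives more. Suppose a fraction p progresses at day 22 (0.72 months) and the rest have a further median of 9 months. The true median is 0.72 + 9 × log2((1 − p)/0.5), which is 8.4, 6.8 or 6.0 months for p = 10%, 20% or 25%. The text rule gives 0.72 + 9 = 9.7 months each time, a difference of 1.4, 2.9 or 3.7 months.

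**49-day rule.** The SAP's window reproduces: 6 × 7 + 7 = 49 days. On an undelayed calendar the two triggers in Section 16.5.4 agree at scheduled visits. PD 42 days after the last adequate assessment means one missed visit and is an event; PD at 63 days means two missed visits and is censored. With a dose delay of d days and assessment only at the delayed cycle start, the gap is 21 + d:

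- d = 28: 49 days, event
- d = 29: 50 days, censored, no visit missed
- d = 42: 63 days, censored, no visit missed

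The smallest triggering delay is therefore 29 days. This takes in part of the 22-42 day category and all of the category above 42 days.

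Size was simulated with 40,000 subjects per scenario, exponential PFS with a true median of 6 months, each cycle independently delayed with the stated probability, no assessment during a delay, 2-year follow-up, and gaps counted from first dose where no adequate assessment exists:

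| Cycles delayed | Median, all events counted (months) | Median, 49-day rule (months) |
|---|---|---|
| None | 6.21 | 6.21 |
| 10%, by 30 days | 6.51 | 7.59 |
| 20%, by 30 days | 6.51 | 9.46 |
| 20%, by 42 days | 6.90 | 10.35 |

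With 20% of cycles delayed 30 days, a true median of 3 months gave 3.45 to 4.44, and of 12 months 12.62 to 19.12. In 2000 trials of 40 (true median 6 months, 20% of cycles delayed 42 days) the rule raised the median in 99% and never lowered it.

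**The case against.** A reader might infer that the plan drops early progressors and early deaths, so that reported PFS is inflated by months. The documents do not support that. Table 5 assigns outcomes situation by situation and counts death before any adequate assessment as an event. It limits day-0 censoring for missing post-baseline assessments to living subjects who have none at all. The PFS definition itself counts first PD. On that reading the day-0 effect is zero, and the 1.4 to 3.7 months above apply only if the text overrides the table, at assumed early-PD rates. This objection stands in full for deaths. For PD at a first scheduled visit it stands less firmly, because the general definition supports an event but Table 5 has no row that names the case.

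On the 49-day rule, the arithmetic needs the assessment to move with the dose. If disease tests are done on the planned day and only the dose is held, the gap to the next assessment is the delay alone, so a 29-day delay would not trigger the rule. Section 16.5.5 allows assessments at unscheduled visits, and visit conduct during delays may be set in the protocol. The delay categories in Section 6.5 are reporting bins and do not forecast that long delays will be common. These points make the finding conditional, but they do not remove the mismatch within Section 16.5.4.

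Finally, PFS is exploratory, single-arm and reported without a test. The planned subject-level PFS and response listings would let a reader trace individual censoring.

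**Conclusion.** There are two defects in the PFS rules.

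The first is an unresolved contradiction between the text and both Table 5 and the PFS definition. It biases median PFS upward only if the text is programmed. The size depends on the early-PD rate, which the SAP does not give: a factor of about 1.07, 1.15 or 1.32 at 5%, 10% or 20% under an exponential curve, and more if early progressors form a separate cluster. Under Table 5 there is no such bias.

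The second is that Section 16.5.4 gives one reason for censoring and applies another trigger. A dose delay of 29 days or more can censor a PD or death although no scheduled assessment was missed, provided none is made during the delay. The direction is upward; the size depends on how often long delays occur, and without delays it is nil. Table 5 also does not say which row governs a death more than 49 days after first dose with no adequate assessment: early death (event) or extended loss (censored).

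No alpha or power figure is affected, so this is not a critical defect. It is worth correcting because median PFS is planned for Part 2 MM and three prior-therapy subgroups, and Section 16.12.6 lists no PFS sensitivity table that would show the effect.

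**What to change.** 1. In Section 7.3.1.2.1, replace the sentence with: *Subjects with no adequate post-baseline assessment who have neither documented PD nor died are censored at first dose.* Make the Table 5 progression row read *at or between scheduled visits*, in line with Table 6.
2. In Section 16.5.4, trigger censoring by the number of scheduled assessments actually missed on the subject's own cycle calendar, not by elapsed days alone. State which Table 5 row applies to a death more than 49 days after first dose with no adequate assessment. Carry the same trigger into TTP and DOR.
3. Add one sensitivity Kaplan-Meier analysis of PFS that counts every PD and death at its actual date.

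The cost is a few lines of SAP wording and one extra table. The reported median PFS may be shorter. No trial procedure changes.

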7.3.1.2.2. Time to Progression

TTP is defined as the interval of time between the date of first dose and the earlier of the date of first documented evidence of PD, or death due to PD, whichever occurs first.

A summary of the assignments for progression and censoring dates for TTP are specified in [Table 6](#)

Table 6 Assignments for Progression and Censoring Dates for TTP Analysis

Situation	Date of Event (Progression/Death) or Censoring	Outcome Event (progression/Death) Or Censored
No (or inadequate) baseline tumor assessments ^[1] and the subject has not died (if the subject has died follow the rules for death indicted at the bottom of the table)	First dose date	Censored
No post-baseline assessments and the subject has not died (if the subject has died follow the rules for death indicted at the bottom of the table)	First dose date	Censored
Progression documented at or between scheduled visits	Date of assessment of progression ^[1]	Event
No progression (or death)	Date of last 'adequate' assessment of response ^[2]	Censored
New anticancer treatment started (prior to documented disease progression or death) ^[3] .	Date of last 'adequate' assessment of response ^[2] (on or prior to starting anti-cancer therapy)	Censored
Death from causes other than progression	Date of death	Censored
Death or progression after an extended loss-to-follow-up time (two or more missed cycles + 7 day window) ^[4]	Date of last 'adequate' assessment of response ^[2] (prior to missed assessments)	Censored

[1] In part 1, adequate baseline assessment is defined as at baseline, a patient has at least one of the following measurements: a. Serum M-protein or b. Urine M-protein or c. Serum FLC assay or d. Biopsy proven plasmacytoma (should be measured within 28 days of Screening Visit).

In part 2, adequate baseline assessment is defined as at baseline, a patient has at least one of the following measurements: a. Serum M-protein ≥ 0.5 g/dL (≥ 5 g/L) or b. Urine M-protein ≥ 200 mg/24h or c. Serum FLC assay: Involved FLC level ≥ 5 mg/dL (≥ 50 mg/L) and an abnormal serum free light chain ratio (<0.26 or >1.65) or d. Biopsy proven plasmacytoma (should be measured within 28 days of Screening Visit and no later than the first dose date).

[2] An adequate assessment is defined as an assessment where the Investigator determined response is sCR, CR, VGPR, PR, MR, or SD.

[3] If PD and New anti-cancer therapy occur on the same day assume the progression was documented first e.g., outcome is progression and the date is the date of the assessment of progression). If anti-cancer therapy is started prior to any adequate assessments, censoring date should be the date of first dose. Refer to Section 16.5.4 "Extended Loss to Follow-up or Extended Time without an Adequate Assessment".

TTP will be summarized using Kaplan-Meier curves. If there are a sufficient number of progressions or death due to PD, median TTP, first and third quartiles and 95% CI, will be estimated using the Brookmeyer-Crowley method [Brookmeyer, 1982]. A figure and listing of TTP time will also be provided. Summary and figure of TTP will be based on Part 2 MM population; listing of TTP will be based on All Treated MM population.

